## 2. ANALYSIS OBJECTIVES

The overall objectives of these analyses are to:

- 1. Describe the pharmacokinetics of daprodustat in adolescent participants with CKD.
- 2. Provide support to the dosing regimen to be used in adolescent participants. Considering that the study enrolled only 4 participants in the adolescent age range, this assessment will be based on all participants (both D and ND subtrial/subpopulation)

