### 4.3. Justification for Dose

In vitro studies have shown that isolated erythroid colony forming units from infants and adults have a similar quantitative response after stimulation by EPO [Rhondeau, 1988]. Similarly, the approved starting doses of rhEPO used to treat anemia associated with CKD are the same in adult and pediatric patients [Aranesp USPI, 2019; Epogen USPI, 2017]. It has been noted that during maintenance treatment of anemia, pediatric patients tend to require higher per kg doses than adult patients [KDIGO, 2012; KDOQI, 2006; Port, 2009], and this is reflected in data collected in the North American Pediatric Renal Transplant Cooperative Study [NAPRTCS, 2011], where the mean weight-normalized dose of rhEPO decreased over increasing age cohorts. Collectively, these data suggest the PK/pharmacodynamic relationship in children with CKD is not expected to be appreciably different to adult patients.

Due to the time-varying ontogeny in the drug metabolism of daprodustat as well as time-varying changes in body weight across age groups, a PBPK approach was utilized to estimate the potential starting doses for the different age groups using a validated PBPK model for daprodustat in healthy adults [GSK Document number 2019N396674\_00]. The PBPK model was derived using the Simcyp Pediatric Absorption Distribution Metabolism Excretion (ADME) Simulator which has 3 components to interrogate the known physiological and biochemical changes in a model to predict PK changes with age in healthy individuals [Abduljalil, 2014]. Therefore, doses for each age group are predicted by matching the pediatric systemic exposure (AUC) of daprodustat to that in adult.

The summary of estimated apparent clearance (dose/AUC) of daprodustat using PBPK in each age group is shown in Table 5, which also shows the predicted ratio of the pediatric to adult dose. Dose proportionality and time-independent PK is assumed when determining the doses in the pediatric population. It should be noted that although these predictions are for healthy individuals, daprodustat PK is generally similar between healthy individuals and renal impairment patients.

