## 4.7. Role of the IDMC in Confirming the Dosing Strategy

The dosing strategy is expected to be the same in either sub-trial (ND/D) and although their Integrated PK Phases will be analyzed and considered independently, the same review and decision making by the IDMC will be required, see also Section 9.4.1.

The IDMC will be responsible for confirming the decision to open up recruitment for each sequential age group (6 to <12 years, 2 to <6 years and 3 months to <2 years) in turn within each sub-trial, and for confirming the following:

- Starting dose in the next younger age group (Section 4.4.2).
- Upper and lower limits of the common dose adjustment algorithm in these age groups (Section 4.5.2).

The IDMC decision will be based (separately for each sub-trial) on the following:

- PBPK model predictions for adult to pediatric dose scaling, confirmed or updated by the actual PK data analyzed after completion in each age group Integrated PK Phase.
- 4-week Hgb and safety data from each age group's Integrated PK Phase.
- Ongoing Hgb and safety data from all participants in each sub-trial.

For the oldest age group (12 to <18 years), the starting dose and dose adjustment algorithm is already pre-defined as the same as in adults. After the 12 to <18 year PK data in the Integrated PK Phase is available, the appropriate pediatric dose ratio to achieve a matching adult exposure to daprodustat is proposed by the GSK study team and provided to the IDMC (i.e., PBPK model predictions are confirmed or the model updated in light of the actual PK data collected). Assuming no concerns from the review of the Hgb response and safety listings during the Integrated PK Phase of the 12 to <18 years, the IDMC will allow:

- Further recruitment into the Main Study of the 12 to <18 years age group.
- Limited recruitment into the study with the Integrated PK Phase of the 6 to <12 years age group, also confirming the dosing strategy (starting dose and dose adjustment algorithm limits) in this age group.

In turn, once the 6 to <12 year Integrated PK Phase data are available and provided no concerns (from Hgb and safety data from their Integrated PK Phase and from the 12 to <18 years age group also in the trial and available to date), the IDMC will permit recruitment into the Integrated PK Phase for the 2 to <6 years age group and also confirm their dosing strategy (starting dose and limits of the dose adjustment algorithm). Finally,

214066 Protocol Amendment 02

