## 1.1.1. Previous Population PBPK Model

A physiologically-based pharmacokinetic (PBPK) model (using the SimCyp® v20.0) of daprodustat (GSK1278863) was developed [3] that successfully predicted pharmacokinetic profiles and parameters across multiple clinical studies in healthy participants. Of note, daprodustat PK in healthy participants and participants with CKD did not show important differences based on the covariate analyses of the population PK models (see Section 1.1.2).

Daprodustat is primarily metabolized by cytochrome P450 (CYP) 2C8 with a minor contribution by CYP3A4. In addition to phase 1 studies in healthy participants, clinical drugdrug interaction (DDI) studies with gemfibrozil (potent CYP2C8 inhibitor) and trimethoprim (weak CYP2C8 inhibitor) were used to identify the relative importance of CYP2C8 pathways in the PBPK model and set relevant pharmacokinetic parameters in the PBPK model. The PBPK model was qualified and verified and demonstrated to be robust and accurate to extrapolate dosing regimens to be adopted in paediatric participants. In particular, PBPK simulations were performed (Simcyp® default), to assess the doses to be used in pediatric participants of different age ranges necessary to match the systemic exposures to daprodustat of adults receiving 2 mg oral single dose. The ratios to adult doses to be adopted in pediatric participants, expected to match the PK doses are reported in Table 1.

Table 1. PBPK-Defined Doses in Participants of Different Age Ranges Necessary to Match the Systemic Exposures to Daprodustat of Adults receiving 2 mg Oral Single Dose

| Age Group a | Dose (mg) | Ratio to Adult Dose |
|------------------------|-----------|---------------------|
| >18 years              | 2.0       | N/A                 |
| 12 to <18 years        | 2.0       | 1                   |
| 6 to <12 years         | 1.0       | 1/2                 |
| 2 to <6 years          | 0.50      | 1/4                 |
| 3 months to <2 years   | 0.25      | 1/8                 |

a. PBPK Simulations conducted with 50 Trials of 10 participants consisting of Pediatric participants falling into the specified age buckets (50% females).

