External validation using the above Phase 1 model appropriately described the Phase 2 data but underpredicted variability. An exploratory evaluation of potential covariate effects was therefore considered more informative than a formal model-based approach. In Phase 2 participants, co-administered clopidogrel or phosphate binder, African-American race, and sex were detected as statistically significant covariates [4].

The Phase 1 daprodustat model was then applied to the prediction of PK data from Japanese CKD patients in Phase 3 clinical studies [5]. In this analysis, the structural model remained the same as that for the Phase 1 analysis, assuming fed conditions (N=7 transit compartments). All parameters were fixed to that in the Phase 1 model, except for ka, KM, F1, and residual error to achieve an acceptable fit in Phase 3 participants. In addition, the effect of HD was not required and was removed from the model.

Lastly, an independent model was developed to describe the PK of daprodustat using data from Phase 2/3 studies in CKD patients receiving HD, PD, or no dialysis (ND) [6]. The structural base model was consistent with that for Phase 1 and comprised a 3-compartment disposition and transit compartment (N=5) absorption. In contrast to previous models, the data did not support estimation of food effects or saturable release (maximum dose 48 mg vs. 300 mg in Phase 1) on absorption parameters. Covariate effects included a reduction in CL with clopidogrel use, and higher ka in non-dialysis dependent participants.

A comparison of parameter estimates from daprodustat population PK models is provided in Table 1 (Appendix).

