## 1.2. Analysis Rationale

The analysis described in the present Study Analysis Plan (SDAP) aims to:

- i) assess the daprodustat PK data emerging from the pediatric study, with the intention to describe the pharmacokinetics of daprodustat in adolescent participants who have evaluable PK data.
- ii) Considering that the study was stopped after enrolment of the first 4 adolescent participants, who were the only participants concluding the study, the analyses also aim to confirm the dosing regimen to be used in cohorts of subjects of adolescents. For this aim, the available daprodustat plasma concentrations (dosenormalized as required) will be projected in a plot together with the reference

Page 10 of 22

plasma concentrations observed in adult participants, defined *via* the PBPK simulation exercise (95%PI) [3]. If ≤50% of observations are outside the prespecified reference levels, the dose algorithm proposed for adolescents will be considered adequate. If instead >50% of observations are outside the prespecified reference levels, model-based simulations based on the population PK model and/or PBPK model may be performed to propose alternative starting dosing regimens, able to more appropriately match the exposures observed in adult participants. The adoption of the starting alternative dosing regimen should be sufficiently flexible considering i) the available dosing strengths, and that ii) daprodustat doses will be anyway modulated using the emerging Hemoglobin data.

This modelling exercise will concern the parent drug, daprodustat. As far as metabolites are concerned, a minimal contribution to daprodustat pharmacology cannot be excluded, but the available information indicate that metabolite contribution to clinical effects is minimal. Indeed, in a cocktail study in mice, the key metabolites of daprodustat showed negligible effect on haemoglobin, haematocrit, and red blood cell count compared to unchanged daprodustat. The PK of metabolites is thus considered out-of-scope in the modelling of paediatric data. Metabolite concentration data will be collected in the paediatric study, but they will simply be described using descriptive statistics.

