## 5.2. Confirmation of Dosing Regimen in Adolescent Participants

[figure not shown]
The criterion used for exploring the consistency between simulated data in adults and plasma concentration data in the available adolescents participants will be that >50% of the observed concentrations in the specified age group of pediatric participants is included in the 95% prediction intervals of the simulated data in adults at 2 mg.

The 95% prediction intervals of the simulated data in adults are shown in Figure 2 (together with simulated observations in a panel of 4 participants); 95% prediction intervals of adult daprodustat plasma concentrations following repeated dose of 2 mg are also reported in Table in the Appendix.

If the consistency between predicted and observed concentration data will be ensured (see Figure 2, where only 4 out of 16, i.e., 25% of the observed plasma concentrations are outside the predefined prediction intervals), the outcome of the previously defined pediatric simulations can be considered adequate. Therefore, it can be concluded that the dosing regimen proposed in adolescents (equivalent to that applied to adult participants) is reasonable. Based on this information, it might also be inferred that the starting dose foreseen by the protocol for participants 6-<12 years old (starting dose of 1 mg QD subsequently titrated based on hemoglobin levels) is reasonable.

If the consistency between observations and predictions will not be ensured, then the popPK model (see Section 5.1) may be used (after suitable modifications, as required) to propose a different dose to be used in adolescents and/or in participants in the lower pediatric age ranges.

Figure 2. Overlay of Simulated Daprodustat Plasma Concentrations in Virtual Pediatric Participants after Repeated Dosing of Daprodustat (Normalized to a Dose of 2 mg QD) on the 95% Prediction Interval of Daprodustat Plasma Concentrations in Adults [3].

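### The 50% concentration check pools dialysis and non-dialysis adolescents, so one sub-trial can lie wholly outside the interval and the dose algorithm still pass

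*SAP*

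**What the plan says.** Section 2 of the population PK plan bound with the SAP pools the two sub-trials for the dosing check: "this assessment will be based on all participants (both D and ND subtrial/subpopulation". The reason it offers is the small number recruited: "Considering that the study enrolled only 4 participants in the adolescent age range". The rule is in Section 1.2: "If ≤50% of observations are outside the prespecified reference levels, the dose algorithm proposed for adolescents will be considered adequate". Section 5.2 restates it as more than half of the observed concentrations lying inside, where inside means that a value "is included in the 95% prediction intervals of the simulated data in adults at 2 mg". That interval is a PBPK simulation (Appendix Table 2), and Protocol 4.3 says the doses were derived "using a validated PBPK model for daprodustat in healthy adults". Section 5.2 provides no overlay or count by sub-trial. From a pass it concludes that the adolescent regimen is reasonable and suggests that the planned starting dose for ages 6 to <12 may be too.

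Elsewhere the unit of comparison is the sub-trial. Protocol 9.3.1 compares each age group with the simulations within each sub-trial. Protocol 4.7 says "The IDMC decision will be based (separately for each sub-trial) on the following". SAP 5.4 and 8.1 promise PK results overall and by sub-trial. SAP Section 14 does not mention a pooled PK check.

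On dialysis effects, PK plan 1.1.1 says that "daprodustat PK in healthy participants and participants with CKD did not show important differences based on the covariate analyses". For the Phase 2/3 model, PK plan 1.1.2 says "Covariate effects included a reduction in CL with clopidogrel use, and higher ka in non-dialysis dependent participants". In Appendix Table 1 the Phase 2/3 column has a row for ND on CL with the value 0.456. The HD-on-CL row reads -0.224, -0.220 and -0.227 (Phase 1 models) and -0.167 (Phase 2).

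**The concern.** The protocol treats D and ND as independent populations, and the comparison exists to show whether adult-equivalent dosing gives adult-like concentrations in each. One pooled share cannot show that. If one sub-trial departs from the interval and the other does not, the conforming samples dilute the departure and a single adequacy statement covers both. The plan's own background makes a difference between D and ND conceivable: its covariate table carries dialysis terms on clearance, and its text and table disagree about the ND term. A pooled count is therefore the display least able to answer the question. The departure from Protocol 9.3.1 is also not recorded where a reader would look for it.

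**Working it through.** **1. The plan's own figure.** Section 5.2 illustrates the rule with 4 of 16 observations outside: 4/16 = 25%. Sixteen fits 4 participants × 4 repeat-dose samples (pre-dose plus three post-dose windows, Schedule of Activities footnote k).

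**2. What pooling does to the count.** With n samples and share p outside in each sub-trial,

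pooled share = (n_D·p_D + n_ND·p_ND) / (n_D + n_ND).

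This is a weighted average of unsigned shares. If both shares exceed 50%, the pooled share exceeds 50%. If only one does, the pool can pass. With 4 samples per participant:

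- Split 3/1, lone participant 4/4 outside, the others 0/12: 4/16 = 25%. Passes, at the same share that Section 5.2 shows as consistent.
- Split 2/2, 8/8 and 0/8: 8/16 = 50%. Passes under Section 1.2. It does not meet Section 5.2, which needs more than half inside, so the two sections disagree at exactly 50%.
- Split 2/2, 7/8 and 0/8: 7/16 = 43.75%. Passes under both wordings, although one sub-trial has 7/8 = 87.5% outside.

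Adding the three Day 1 samples gives 7 per participant and 28 in all; the lone participant then contributes 7/28 = 25%, the same share.

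**3. What the printed covariates imply, each within its own model.** AUC ratio = 1/(1 + effect), reading effects as proportional.

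- HD: clearance 16.7% to 22.7% lower, so 1/(1 - 0.167) = 1.20 to 1/(1 - 0.227) = 1.29.
- ND, if 0.456 acts on CL: 1/1.456 = 0.69, or exp(-0.456) = 0.63 if it is on the log scale (the row does not say).
- ND, if the effect is on ka as Section 1.1.2 says: AUC ratio 1.00.

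**4. Would shifts of that size trip the rule?** The interval is very wide. From Appendix Table 2, upper/lower limit is 73.11/6.71 = 10.9 at 1 h, 36.26/0.498 = 72.8 at 4 h and 0.10584/0.000391 = 270.7 at trough. Its median profile integrates (trapezoid) to 66.4, against 2000/31.7 = 63.1 from the adult clearance in Protocol Table 5, which fits a healthy-adult reference.

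For illustration, a split-lognormal was fitted to the printed percentiles and typical profiles were taken from the Phase 1 parameters, with samples at trough, 1 h, 2.25 h and 4 to 8 h. The expected share outside is 5% with no shift, about 6.5% if all are HD (-22.7%) and about 10% to 12% if all are ND (+45.6% on CL). The binomial probability of 9 or more of 16 outside is below 0.00003 in each case. Under a uniform shift, five times the reference concentration gave 43% outside and eight times gave 56%; one quarter gave 32% and one tenth gave 67%.

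**The case against.** The pooling is disclosed and has a reason: four participants. The protocol's minimum is four with PK data per age group in each sub-trial, so if both sub-trials are represented every split count falls below it. Protocol 4.7 governs IDMC decisions to open age groups, and recruitment has ended. SAP 2.2 announces one final analysis for both sub-trials combined. The population model to be run is the comprehensive one, which keeps dialysis type on ka and CL and re-estimates it (PK plan 1.1.3 and 5.1), so the ka/CL conflict sits in background text and does not by itself determine the AUC reported for ND.

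Most of this stands. It justifies a pooled display and argues against treating the conflict as a modelling error. It does not justify dropping the split display. SAP 2.2 concerns the number and timing of analyses, and SAP 8.1 still promises PK results by sub-trial. Protocol 9.3.1 is a statistical rule, separate from the IDMC procedure, and Section 5.2 still draws a dosing conclusion from the count.

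A reader might infer that high exposure in D and low exposure in ND cancel in the pooled count, so that two deviating sub-trials could pass. They cannot: excursions in either direction both count as outside, so they add, and two shares above 50% cannot average to 50% or less.

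A reader might also take ND clearance to be 46% higher, or combine the HD and ND terms into one contrast. The documents support neither. The 46% is a table row contradicted by the text on the same model, and the HD and ND terms come from different models. The Japanese Phase 3 model needed no HD effect, and the D sub-trial includes peritoneal dialysis, so higher exposure in D as a whole is not established.

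**Conclusion.** The point holds as dilution together with an unrecorded departure from the protocol. One sub-trial can have every sample outside the interval while the pooled share is 25% or 50%, and Section 1.2 calls both adequate. This rests on 4 samples from each of 4 participants and on hypothetical splits, because the documents do not give the actual D/ND split; if all four were in one sub-trial, nothing would be diluted.

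The size should not be overstated. Shifts as large as the printed HD or ND effects would rarely move the 50% rule, pooled or split, so splitting is unlikely to reverse the formal result. Its value is that each population is seen separately. That calculation assumes sampling times within the windows, proportional covariates, linear absorption at 2 mg and independent samples.

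Two secondary documentation points also hold. PK plan 1.1.2 and Appendix Table 1 conflict on the ND effect. The unqualified statement in 1.1.1 is broader than a table showing HD clearance 17% to 23% lower, although the evidence is mixed.

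**What to change.** - In PK plan 5.2, keep the pooled overlay and count, and add the same overlay and in/out count for D and for ND.
- Word the adequacy conclusion per sub-trial and as descriptive only.
- List the pooled comparison, with its reason, as a change from Protocol 9.3.1 in SAP Section 14.
- Make PK plan 1.2 and 5.2 agree on the outcome at exactly 50%.
- Check the Phase 2/3 source report, correct whichever of PK plan 1.1.2 and Appendix Table 1 is wrong on ND, and state the scale of the 0.456.
- Qualify the statement in PK plan 1.1.1 by citing both the HD terms in the table and the Japanese Phase 3 model that dropped the HD effect.

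The cost is some wording and one extra panel, with no new data and no change to dosing. The drawback is that each sub-trial count rests on very few samples, possibly four from one person, so it can describe but not confirm.

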## 3. STUDY DETAILS

The available data from the GSK214066 study will be included in this population PK analysis. Whilst the study was designed to have a staggered enrollment of the pediatric participants of different age groups (adolescents, i.e., 12-<18 years, followed by participants with 6-<12 years, 2-<6 years, and 3 months-<2 years) (see Section 1.1), eventually the study enrolled only 4 adolescent participants before being stopped.

A summary of the clinical study as it was originally designed is provided in Table 2.

Table 2 Summary of the GSK214066 Study

| Study,
Phase     | Description  | Population  | Dose Regimen No. of Participant  | Sampling   |
|---------------------|--|---|--|--|
| 214066,
Phase 3a | An Integrated Pharmacokinetic and Safety Open-label Basket Trial of Daprodustat for the Treatment of Anemia Associated with Chronic Kidney Disease in Male and Female Children and Adolescents Aged 3 Months to Under 18 Years Requiring | Pediatric CKD patients with anemia requiring (D) or not requiring (ND) dialysis. D substudy/ subpopulation will enroll in both Japan and US; ND substudy/ subpopulation will enroll in Japan only | Assuming the PBPK model predictions are appropriate and unchanged by the PK data collected and analyzed during the study in the Integrated PK Phase, the starting dosing in the younger age groups is also provided in the following tables based on the predicted scaling (ratio of adult to pediatric dose) reported below.  Apparent Oral Clearance of Daprodustat by Age Group and Predicted Dose Equivalent to a 2 mg Adult Dose    Age Group | collected at pre-
dose
0.5 -1.5 hour,
>1.5 to 3 hour,
≥4 (≤8) hours
post-dose.
Samples |

Page 12 of 22

14 July 2025 74

| Study,
Phase | Description | Population | Dose Regimen   |  |  |  |  |                                | No. of Participants        | Sampling |  |
|-----------------|-------------|------------|--|--|--|--|--|--------------------------------|----------------------------|----------|--|
|                 |             |            | Starting Dose of Daprodustat in E Dialysis  Prior ESA dose at Baseline Epoetins (incl   Darbepoetin   Methoxy PEG-   |  |  |  | ers, Un  | dose per a                     |                            |          |  |
|                 |             |            | biosimilars)
(convert SC to
IV U/week) a  | ert SC to (µg/4wk  | epoetin beta
(µg/month
SC/IV) c,d   | Adults
and 12 to
<18 years                                       | 6 to <12
years                                  | 2 to <6
years               | 3 months
to <2
years |          |  |
|                 |             |            | ≤2000°
>2000 to
<10,000  | ≤30
>30 to 150  | ≤40
>40 to 180  | 6  | 3  | 1.5                            | 0.5
0.75                |          |  |
|                 |             |            | ≥10,000 to <20,000 ≥20,000 Abbreviations: PEG a. Standard rhEPC b. Conversion of 2 [Sterner, 2008]. c. Conversion of 1 dose strength [6 d. Conversion of 2 | O IV dose (U/week
50U:1μg (epoetin
:1.2 μg (darbepoe
Choi, 2013].
08 U:1 μg (epoetin | >180 to 360  >360  ol. SC = subcutanec ) = 161/113 x (epoeti ) (v.darbepoetin alfa) u tin alfa:methoxy PEG of to V:methoxy PEG-ep of dose / dose-hold at | SC dose (units
tilized and round
epoetin beta) ut
petin beta) | ))/(frequency
ded to the nea
tilized and rou | ) [Besarab, 2
arest availab | 2002].
le dose strength |          |  |

Abbreviations: CKD = chronic kidney disease; D=dialysis ESA = Erythropoiesis-stimulating agents; ND = no dialysis; PBPK=physiology-based pharmacokinetic model; PK = pharmacokinetics; QD = once daily.

